Subjects will be informed that it is not necessary for subjects to participate in this study in order to treat their IC/PBS. Subjects will also be informed that there are other treatments available in the community including physical therapy techniques and pharmacotherapies with side effects and efficacy that may be equivalent to, better or worse than what the subject may experience in this study. This will be discussed prior to enrollment into the study. If patients choose not to enroll in this study but have symptoms for which PTNS is indicated, they may still receive this as a possible therapy.

SECTION 9: ADVERSE EVENT REPORTING/MANAGEMENT AND COMPENSATION FOR INJURY

A. Adverse Events and Unanticipated Problems

1. Indicate that you are familiar with **UCI's Adverse Events/Unanticipated Problems** reporting policy and procedures. See <http://www.research.uci.edu/compliance/human-research-protections/researchers/reporting-of-adverse-events-unanticipated-problems-and-violations.html> for details.

Although this study involves no interaction/intervention with research subjects (i.e., involves the use of records, charts, biospecimens) an unanticipated problem may still occur (e.g., a breach in confidentiality), the researchers are aware of UCI's Unanticipated Problems involving Risk to Participants or Others reporting policy and procedures and will comply with this policy.

This study involves interaction/intervention with research subjects. The researchers are aware of UCI's Unanticipated Problems involving Risk to Participants or Others reporting policy and procedures and will comply with this policy.

2. **If this study involves interaction/intervention with research subjects**, explain how the research team will **manage adverse events and unanticipated problems** that may occur during the study or after completion of the study (i.e., provide a plan).

Not applicable - This study involves **no interaction/intervention** with research subjects (i.e., involves the use of records, charts, and/or biospecimens).

OR

If an adverse event occurs during the study, the steps are as follows:

- 1) Subject informs the physician, clinic nurse or another research team member of the possible adverse event.
- 2) Study physician determines if it is, in fact, an adverse event that is related to the study protocol.
- 3) Physician decides an appropriate medical response within a reasonable timeframe. This includes coordinating urgent care if indicated.
- 4) The adverse even is reported appropriately within the timeframe noted below depending on the nature of the adverse event.

Unexpected, related adverse events will be reported to the IRB via the electronic, online reporting process as soon as possible, but not later than 10 working days after the research team first learns of the event. Serious adverse events will be reported in the same manner as soon as possible but not later than 48 hours after the researcher first learns of the event, followed by any follow-up reports as applicable.

All adverse events will be followed to appropriate resolution. Where appropriate, medical tests and examinations are performed to document resolution of event(s).

B. Compensation for Injury

For **Full Committee protocols**, explain how costs of treatment for research related injury will be covered.

[] Not applicable - This study involves no more than minimum risk and qualifies as **Expedited research**.

[X] Researchers are familiar with and will follow UC policy regarding treatment and compensation for injury. If subjects are injured as a result of being in the study, UCI will provide necessary medical treatment. The costs of the treatment may be covered by the University of California, the study sponsor, or billed to subject or the subject's insurer just like other medical costs, depending on a number of factors. The University and the study sponsor do not normally provide any other form of compensation for injury.

[] Other: <Type here>

SECTION 10: PARTICIPANT COSTS

1. If subjects or their insurers will be charged for study procedures, **identify and describe those costs**.
2. Explain why it is **appropriate to charge those cost** to the subjects or their insurers. Provide supporting documentation as applicable (e.g., FDA Device letter supporting charges).

[] Not applicable - This study involves no interaction/intervention with research subjects (i.e., involves the use of records, charts, biospecimens).

[] There are no costs to subjects/insurers.

OR

PTNS is an FDA approved device for the treatment of “urinary urgency, urinary frequency and urge incontinence.” It is typically a covered benefit of health insurance as a second line treatment for these complaints and all subjects will be required to qualify for PTNS based on the FDA approved indications of urinary frequency and urgency.

SECTION 11: PARTICIPANT COMPENSATION AND REIMBURSEMENT

1. If subjects will be compensated for their participation, explain **the method/terms of payment** (e.g., money; check; extra credit; gift certificate).
2. Describe the **schedule and amounts of compensation** (e.g., at end of study; after each session/visit) including the total amount subjects can receive for completing the study.
3. Specify whether subjects will be **reimbursed for out-of pocket expenses**. If so, describe any requirements for reimbursement (e.g., receipt).

Note: Compensation should be offered on a prorated basis when the research involves multiple sessions.

Not applicable - This study involves no interaction/intervention with research subjects (i.e., involves the use of records, charts, biospecimens).

No compensation will be provided to subjects.

No reimbursement will be provided to subjects.

OR

If the subject completes 12 treatment visits and returns the subsequent 24 hour voiding diary and questionnaires, they will receive a \$50 stipend (cash or gift card). No other compensation or stipends will be provided for in the study.

SECTION 12: CONFIDENTIALITY OF RESEARCH DATA

1. Indicate all identifiers that may be included in the research records for the study. Check all that apply:

Note: If this information is being derived from a medical record; added to a medical record; created or collected as part of health care, or used to make health care decisions it qualifies as PHI under HIPAA. The subject's HIPAA Research Authorization is required or a waiver of HIPAA Authorization must be requested (Appendix T).

No subject identifiers are obtained (i.e., researchers will not collect information that can link the subjects to their data)

OR

| | | |
|---|--|--|
|  Names |  Social Security Numbers |  Device identifiers/Serial numbers |
|  Dates* |  Medical record numbers |  Web URLs |
|  Postal address |  Health plan numbers |  IP address numbers |
|  Phone numbers |  Account numbers |  Biometric identifiers |
|  Fax numbers |  License/Certificate numbers |  Facial Photos/Images |
|  Email address |  Vehicle id numbers |  Any other unique identifier |
|  Other (Specify all): <Type here> | | |

| |
|--|
| 
* birth date, treatment/hospitalization dates
 
2. Explain how data will be recorded.
 |
| 
Check all that apply:
 
  Paper documents/records  Electronic records/database  Audio recording  Video recording  Photographs  Biological specimens  Other(s) (specify): <Type here> 
 |
| 
3. Indicate how data will be stored, secured including paper records, electronic files, audio/video tapes, biospecimens, etc.
 
Note: If the research data includes subject identifiable private information and/or Protected Health Information, the storage devices or the electronic research files must be encrypted.
 |
| 
Electronic Data (check all that apply):
 
  Coded data; code key is kept separate from data in secure location.  Data includes subject identifiable information. Note: Encryption software is required. (Provide rationale for maintaining subject identifiable info): <Type here>  Data will be stored on secure network server.  Data will be stored on stand alone desktop computer (not connected to network/internet)  Other (specify here): <Type here> 
 |
| 
Hardcopy Data, Recordings and Biospecimens (check all that apply):
 
  Coded data; code key is kept separate from data in secure location.  Data includes subject identifiable information (Provide rationale for maintaining subject identifiable info): <Type here>  Data will be stored in locked file cabinet or locked room at UCI/UCIMC.  Data will be stored locked lab/refrigerator/freezer at UCI/UCIMC.  Other (specify here): <Type here> 
 |
| 
Data on Portable Devices:
 
4. Describe the portable device(s) to be used (e.g. laptop, PDA, iPod, portable hard drive including flash drives).
 
5. Specify whether subject identifiable data will be stored on the device. If so, justify why it is necessary to store subject identifiers on the device.
 
Note: Only the “minimum data necessary” should be stored on portable devices as these devices are particularly susceptible to loss or theft. If there is a necessity to use portable devices for initial collection of identifiable private information, the portable storage devices or the research files MUST BE ENCRYPTED, and subject identifiers transferred to a secure system as soon as possible.
 |

Not applicable – No study data will be maintained on portable devices.

Data Access:

6. Specify who, besides the entities listed below, will have **access to subject identifiable private data and records**.
7. If there is a **code key**, specify who on the research team will hold the key, and who will have access to the key.
8. If publications and/or presentations will include **subject identifiable information**, specify where the data will be **published and/or presented** and address how the study team will obtain permission from subjects.

Note: Authorized UCI personnel such as the research team and the IRB, the study sponsor (if applicable), and regulatory entities such as the Food and Drug Administration (FDA) and the Office of Human Research Protections (OHRP), may have access to study records to protect subject safety and welfare. Any study data that identifies the subjects should not be voluntarily released or disclosed without the subjects' separate consent, except as specifically required by law. Publications and/or presentations that result from this study should not include subject identifiable information; unless the subject's separate consent has been obtained.

Not applicable – No subject identifiers will be collected.

Not applicable – Only the entities listed above will have access to subject identifiable private data and records.

<Type here>

Data Retention:

9. Explain **how long subject identifiable research data** will be **retained**. The data may include a code with a separate code key or the data may include subject identifiers.

Notes:

- **If more than one of the options below is applicable** [e.g., the study involves children], **records should be kept for the longer period**.
- **Research documentation involving Protected Health Information (PHI) should be retained for six years** (e.g., IRB documentation, consent/assent forms – **NOT** the actual PHI). **Investigators must destroy PHI at the earliest opportunity, consistent with the conduct of this study, unless there is an appropriate justification for retaining the identifiers or as required by law.**

- Not applicable. No subject identifiable research data will be retained.
- Destroy once data collection is completed
- Destroy at the earliest opportunity, consistent with the conduct of this research. Specify timeframe: <Type here>
- Destroy after publication/presentation
- Maintain for approximately <Type here> years. (e.g., 3 months, etc.)
- Maintain in a repository indefinitely. Other researchers may have access to the data for future research. Any data shared with other researchers, will not include name or other personal identifying information. Note: **Appendix M is required.**
- Research records will be retained for seven years after all children enrolled in the study reach the age of majority [age 18 in California] as this study includes children .
- Research records will be retained 25 years after study closure as this study involves in vitro fertilization studies or research involving pregnant women.
- As this is a FDA regulated study, research records will be retained for two years after an approved marketing application. If approval is not received, the research records will be kept for 2 years after the investigation is discontinued and the FDA is notified.
- Other: <Type here>

Data Destruction:

10. If audio or video recordings will be taken, specify the **timeframe for the transcription and/or destruction of the audio and video recordings.**
11. If photographs will be collected, specify the **timeframe destruction of photographs.**

- Not applicable – No audio/video recordings or photographs will be collected.
- Audio or video recordings transcribed; specify time frame: <Type here>
- Audio or video recordings destroyed; specify time frame: <Type here>
- Audio or video recordings maintained indefinitely
- Photographs destroyed; specify time frame: <Type here>
- Photographs maintained indefinitely

Certificate of Confidentiality:

12. Specify whether a Certificate of Confidentiality (COC) has been or will be requested from the NIH. If yes, explain in what situations personally identifiable information protected by a COC will be disclosed by the UCI study team.

Note: If the COC has been secured a copy of the COC Approval Letter should accompany the IRB application or be provided to the IRB upon receipt.

- Not applicable – No COC has been requested for this study.

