This is a pilot study with primary aim to estimate the proportion of patients experiencing moderate or marked improvement in overall symptom score as measured by response to a 7-point global response assessment scale collected after the intervention period. Responders will be defined as those reporting a moderate or marked improvement in symptoms in global response score. We will estimate the proportion of responders with 95% confidence limits, as defined by a response of moderate or marked improvement on the GRA scale collected at follow-up. Pain response will be measured using the Pelvic Pain and Urgency/Frequency Patient Symptom Scale (score total range: 0-35). We will estimate mean (plus standard deviations and 95% CI) for pain score at baseline and follow-up and change in response to therapy, testing for change over time using a paired t-test.

Other secondary outcomes that we will be reviewing are: change in frequency of urinary collected in 24 hour voiding diaries, change in visual analog scale, and change in O'Leary-Sant IC Symptom and Problem Index. These data consist of continuous variables to be described using means, SDs and confidence intervals at baseline and follow-up. Change over time will also be estimated and tested for difference from zero using a paired t-test.

SECTION 4: SUBJECTS (PERSONS/CHARTS/RECORDS/SPECIMENS)

A. Number of Subjects (Charts/Records/Biospecimens)

- Indicate the **maximum number of subjects to be recruited/consented** on this UCI protocol. This is the number of potential subjects you may need to recruit to obtain your target sample size. This number should include projected **screen failures and early withdrawals**. *Note: The IRB considers individuals who sign the consent form to be "enrolled" in the research.*
- For **Mail/Internet surveys** include the number of people directly solicited.
- If the study involves use of **existing charts, records, biospecimens**, specify the maximum number that will be reviewed/tested to compile the data or the sample population necessary to address the research question.

32

- Of the maximum number of subjects listed above, indicate the **target sample size** for the study. This is the number of subjects expected to complete the study or the number necessary to address the research question.

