5. For social/behavioral research, the maximum sample size is often similar to the target sample size. If the **maximum sample size** is significantly greater (i.e., $\geq 1.5x$) than the **target sample size** provide a justification.
6. For studies where multiple groups of subjects will be evaluated, **provide a breakdown per group** (e.g. controls vs. experimental subjects; children vs. adults; by age group).

24

7. For **multi-center research**, indicate the overall sample size for the entire study (across all sites).

Not applicable - This study is not a multi-center research study.

8. Demonstrate that the **target sample size will be sufficient** to achieve the study goal and should coincide with the statistical approach **described in Section 3B**. **Note: Required for scientific review.**
9. **Sources and information** of assumed group effects and variability should be supplied (e.g., pilot data; data from related literature). **Note: Required for scientific review.**

This is a pilot study with a primary aim to estimate the proportion of patients experiencing moderate or marked improvement in overall symptom score. With a target sample size of 24 patients, 95% confidence limits will extend ± 0.2 from the estimate. If the estimated improvement rate is 60%, the 95% CI will extend from 40% to 80%, indicating that there is a 95% probability that the true percent experiencing moderate or marked improvement is $\geq 40\%$. This response rate would be of clinical importance.

The maximum number of subjects to be recruited was determined at 32, assuming a 33.3% rate of exclusion or withdrawal by subjects enrolled in the study that will allow for obtaining the target sample size.

B. Inclusion and Exclusion Criteria

1. Describe the **characteristics and provide justification** for inclusion of the proposed subject population. At a minimum include information about the age and gender of the study population.
2. Describe **different subject groups** (e.g., students and teachers; control group and treatment group(s), children and adults) separately.

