While subjects will be restricted from receiving new additional standard therapies during the course of the study, there is very limited risk associated with this because they will only be restricted during the course of the study protocol. Patients will be permitted to continue standard of care oral medical therapies (such as pyridium, Elmiron, or other medications considered second line in the AUA guidelines for treatment of IC/PBS) if they had been receiving this medication prior to enrollment in the trial protocol. If they so choose, they will be able to receive any other additional indicated treatments immediately following conclusion of the trial protocol. If they choose to withdraw from the study in order to receive another indicated (standard) therapy that will be noted and included in our results. Any subject who withdraws will be offered an appointment with her physician.

PHI will be collected as part of this study. Breach of confidentiality is a theoretical risk.

5. Discuss what steps have been taken and/or will be taken to **prevent and minimize** any risks/ potential discomforts to subjects (address physical risks as well as other risks such as the potential for a breach of confidentiality). Examples include: designing the study to make use of procedures involving less risk when appropriate; minimizing study procedures by taking advantage of clinical procedures conducted on the subjects; mitigating risks by planning special monitoring or conducting supportive inventions for the study.

All subjects will be carefully monitored throughout the study protocol. They will have weekly visits with a trained, urogynecology practitioner who will be administering the PTNS treatments. This provider is qualified to assess and triage complaints related to the PTNS procedure and will contact the appropriate research physician if additional assessment is indicated. The practitioner administering the PTNS treatments will work with the subject, in the standard fashion for PTNS, to minimize any transient discomfort during the treatments.

Subjects may return to UCIMC urogynecology clinic for additional visits outside of the study protocol at their own discretion, if there are any complaints they feel need to be assessed by a physician. We will work to minimize inconvenience associated with study participation by allowing the subject to schedule the PTNS treatments at the time most convenient for them, within clinic scheduling ability.

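### A cap of 32, a target of 24 and a 33.3% loss among enrolled subjects cannot all hold: that loss leaves about 21, and 32 allows for only 25%

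*Combined protocol and SAP*

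**What the plan says.** All the figures are in Section 4A, Number of Subjects.

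- **Maximum to be recruited or consented:** 32. The form asks that this number include projected screen failures and early withdrawals, and adds: "The IRB considers individuals who sign the consent form to be" enrolled.
- **Target sample size:** 24. The form explains the entry: "This is the number of subjects expected to complete the study or the number necessary to address the research question".
- **Precision at the target:** "With a target sample size of 24 patients, 95% confidence limits will extend" 0.2 either side of the estimate. The worked example is an estimate of 60% with an interval from 40% to 80%.
- **Link between the two numbers:** the cap is given as "determined at 32, assuming a 33.3% rate of exclusion or withdrawal by subjects enrolled in the study". The plan then claims that 24 can be reached on this basis.

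Two other places bear on the point. The chronological description of study activities puts screening against the eligibility criteria after consent is signed. Section 7B says of subjects who leave for another standard "therapy that will be noted and included in our results".

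**The concern.** The sentence linking 32 to 24 names its own denominator: subjects enrolled in the study. By the form's definition these are the people who signed consent. Because screening follows consent, subjects excluded at screening are already inside the 32. The 33.3% is therefore a share of the 32, and a third lost from 32 does not leave 24.

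This sentence is the only support the plan gives for the recruitment maximum. If the stated loss rate is what the team expects, the study would be expected to finish below its own target, with a wider interval than the one given in its sample size justification. If a different denominator was meant, the stated rate is wrong. The documents do not settle which.

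**Working it through.** **Inputs (all Section 4A):** maximum N = 32; target n = 24; loss rate d = 33.3%, taken as 1/3, among enrolled subjects; precision ±0.2, illustrated at 60%.

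**1. How 32 arises.** Applying the rate to the target gives n × (1 + d) = 24 × 4/3 = 32. This matches the stated maximum exactly. The 8 extra subjects are 8/24 = 33.3% of the target, but 8/32 = 25% of those enrolled.

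**2. What the sentence says as worded.** Applying the rate to the enrolled gives N × (1 − d) = 32 × 2/3 = 21.3, so about 21 and not 24.

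**3. Largest loss that 32 can absorb.** 1 − 24/32 = 25%.

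**4. Reverse check.** The number to enrol so that 24 remain after losing a third is n/(1 − d) = 24/(2/3) = 36, which is 4 more than stated.

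**5. Effect on precision.** The Wald half-width, 1.96 × √(p(1 − p)/n), reproduces the plan's own ±0.2 and is used for the comparison.

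| n | p | Half-width | Interval |
|---|---|---|---|
| 24 | 0.5 | 0.200 | 30.0% to 70.0% |
| 24 | 0.6 | 0.196 | 40.4% to 79.6% |
| 21 | 0.5 | 0.214 | 28.6% to 71.4% |
| 21 | 0.6 | 0.210 | 39.0% to 81.0% |

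At 60%, each end moves by about 1.4 percentage points.

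**6. Sensitivity to the interval method.** Wilson limits at 60% are 40.4% to 76.9% for n = 24 and 39.1% to 77.8% for n = 21. The lower limit falls by about 1.3 points, so the change is of similar size.

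The 60% is nominal, as in the plan: 0.6 × 24 = 14.4 and 0.6 × 21 = 12.6 are not whole numbers of patients.

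**The case against.** **It is probably a wording slip.** Since 24 × 1.333 gives 32 exactly, the likeliest explanation is that 33.3% is the over-recruitment margin on the target, misdescribed as a rate among enrolled subjects. The cap and target would then be as intended. This is a fair inference, and it limits the consequence. It does not make the sentence correct, and no source for the 33.3% is given that would confirm it.

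**Little depends on it.** This is a single-arm pilot whose primary aim is estimation. The primary outcome has no hypothesis test and no go/no-go threshold. The precision statement is conditional on 24 patients, so it remains approximately true for 24 whatever the loss rate. All of this stands. What is affected is whether 24 can be expected under the cap.

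**The shortfall may be smaller than three.** Section 7B says withdrawals to another standard therapy are included in the results. If some of those subjects count in the responder denominator, more than 21 would be analysed. That is possible, but the statement may mean only that withdrawals are reported, and the Section 4A sentence itself treats excluded and withdrawn subjects as not counting toward 24.

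**A cap of 36 would keep both the 33.3% and the 24.** This is arithmetically true. It means enrolling more patients, which the inconsistency alone does not require. It would also be exactly 1.5 times the target, the ratio at which the form, in an item worded around social and behavioral research, asks for a justification.

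**Conclusion.** The inconsistency is real and the three figures cannot stand together as written. With 33.3% loss among the 32 enrolled, about 21 subjects are expected; for 24 to remain, the loss can be at most 25%. Either the base of the percentage or the cap is wrong.

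The size is modest. Under the over-recruitment reading the expected number stays at 24 and nothing but the wording changes. Under the literal reading it falls to 21.3, and the half-width rises from 0.196 to 0.210 at 60% (0.200 to 0.214 at 50%). The lower limit in the plan's example then falls just under 40%, but the plan has no rule that it must reach 40%, so no decision changes.

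The figure of 21 assumes that enrolled has the form's meaning and that excluded and withdrawn subjects do not count toward the target. The point should be fixed because the error is certain and the correction is very cheap.

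**What to change.** Correct the sentence in Section 4A so that the cap, the target and the loss rate agree, in whichever way matches the team's real expectation:

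- **(a)** If 24 is still the expected number, state that 32 allows for 25% exclusion or withdrawal among enrolled subjects (8 of 32).
- **(b)** If a loss of 33.3% of enrolled subjects is the real expectation, keep 32, say that the expected evaluable number is about 21 and thus below the stated target of 24, and restate the precision as about ±0.21 (roughly 39% to 81% at 60%).

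Option (a) costs one corrected sentence; option (b) also changes the precision sentence. Neither needs additional patients or procedures.

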The primary outcome variable will be the percentage of subjects to report that they are moderately improved or markedly improved in overall symptoms compared to baseline on a 7-point global response assessment (GRA) scale. The GRA scale involves asking the question, "As compared to when you started the current study, how would you rate your overall symptoms now?". There are 7 possible responses: markedly worse, moderately worse, slightly worse, the same, slightly improved, moderately improved and markedly improved. This scale is the current standard for outcome in studies that are evaluating treatments and interventions for IC/PBS.

There will be a number of secondary outcome variables including: changes in a 24 hour voiding diary during the course of the interventions, ratings for bladder pain, urinary urgency and urinary frequency on standardized scales, the score on O'Leary-Sant IC Symptom and Problem Index, scores validated questionnaires for pelvic floor, sexual dysfunction and general health and any reports of adverse events.

The study will also examine demographic data and information on the course of the disease in subjects.

4- Existing Knowledge:

There are few published studies looking at PTNS and IC/PBS. Literature review identified six studies that evaluated the effect of PTNS on pain syndromes. Four of these studies looked at chronic pelvic pain^{5,6,7,8}, one study evaluated chronic prostatitis/chronic pelvic pain in men⁹ and only a single study examined PTNS in patients with IC/PBS¹⁰. However, in the study of IC/PBS, there was a nonstandard treatment course (10 instead of 12 sessions of PTNS), the subjects had severely refractory IC/PBS with multiple prior treatments attempted in all cases and often long-standing disease (up to 22 years). By only examining highly refractory subjects, the potential benefit of a minimally invasive intervention early in the disease process may have been missed.

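### Section 9A settles whether an event is adverse and whether it is related in one decision before reporting, and leaves no path for events judged unrelated

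*Combined protocol and SAP*

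**What the plan says.** Section 9A (Adverse Events and Unanticipated Problems) sets out a sequence.

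- Step 1: "Subject informs the physician, clinic nurse or another research team member of the possible adverse event".
- Step 2: "Study physician determines if it is, in fact, an adverse event that is related to the study protocol".
- Step 3: the physician decides on a medical response.
- Step 4: "The adverse even is reported appropriately within the timeframe noted below depending on the nature of the adverse event".

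Two reporting rules follow. For the first, "Unexpected, related adverse events will be reported to the IRB via the electronic, online reporting process as soon as possible", with a limit of 10 working days. The second reads "Serious adverse events will be reported in the same manner as soon as possible but not later than 48 hours after the researcher first learns"; its clock thus starts at first knowledge. The section adds that all adverse events are followed until they resolve.

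Section 1, item 3 (Outcomes) lists "any reports of adverse events" among the secondary outcomes, with no condition on cause. The chronological description of study activities has the nurse ask, at the treatment visits, about adverse reactions to the treatment. The visit table likewise lists adverse reactions as information obtained at visits 1 to 12. Section 3B (Statistical Considerations) does not define, code or analyse adverse events.

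**The concern.** Whether something untoward happened is a matter of fact; whether the stimulation caused it is a judgement. Safety recording normally keeps the two apart so that the judgement can be reviewed later. Step 2 combines them and places the result ahead of reporting. An event judged unrelated has no stated destination: the steps do not say whether it is recorded, counted or reported.

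Two things are at stake. The first is oversight: a serious event that the study physician attributes to something else could fail to reach the IRB. The second is the secondary outcome. The nurse's question invites only complaints that the woman or the nurse already links to the treatment. A worsening of bladder symptoms, for example, is easily put down to the underlying disease and may not be mentioned or written down. With one arm there is no control rate against which to judge the count, so its completeness matters more.

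**Working it through.** The point is textual. The plan gives no adverse-event figure to reproduce, so the check is to set the texts side by side and trace events through them.

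**1. Reporting.** Section 9A can be read in two ways.

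- Reading A: the steps apply in order, so only an event that passes step 2 reaches step 4.
- Reading B: the two reporting rules stand alone, and step 2 merely describes the physician's assessment.

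| Event | Reading A | Reading B |
|---|---|---|
| Serious, judged related | reported within 48 hours | reported within 48 hours |
| Serious, judged unrelated | stops at step 2 | reported within 48 hours |
| Not serious, unexpected, judged related | reported within 10 working days | reported within 10 working days |
| Not serious, judged unrelated | stops at step 2 | outside both rules |

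For IRB reporting the readings part in one row only: the serious event judged unrelated. They also differ on timing for any serious event. Under A the report waits for a judgement, while the 48-hour clock is already running from first knowledge. In the last row neither reading leads to a report, and neither says whether the event is recorded.

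**2. Evidence within the section.** The 10-day rule names events that are both unexpected and related. If step 2 had already removed unrelated events, the word for relatedness would do no work there. The 48-hour rule carries no such word. Both facts favour reading B. The numbered order of the steps favours reading A. Nothing in the text says which governs.

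**3. The secondary outcome.** Section 1 refers to any reports and does not cite Section 9A. The collection route described is the nurse's inquiry at visits 1 to 12, and both the visit descriptions and the visit table confine it to reactions. Collection is therefore narrowed by presumed cause at the moment of asking, whichever reading of step 2 is taken.

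**4. Scale.** The target is 24 women and the maximum recruited is 32. One woman whose event is not recorded shifts the proportion with any event by 1/24 = 4.2 percentage points, or by 1/32 = 3.1 points. The number who will have had at least one session is not given; 24 to 32 is taken here as the range. How many events would be lost cannot be derived from the documents.

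**The case against.** The strongest reply is that Section 9A answers a form prompt on managing events and reporting them to the IRB, and does not define an outcome. Its specific reporting rule for serious events is unconditional and timed from first knowledge, and a specific rule would ordinarily prevail over a loosely worded step. The team also commits to the institution's reporting policy, and the data collection instruments are attached to the protocol. Neither is available here, and either may already separate the fields. Worsening symptoms would also show in part on the global response scale and on the pain scale completed at treatment visits.

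Much of this stands, and it rules out several stronger readings that a reader might infer.

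- That an event is an adverse event only if judged related: no text defines it so, and the 10-day rule implies otherwise.
- That the secondary outcome is whatever passes step 2: no sentence makes that link.
- That the treating practitioner screens events out beforehand, because Section 7B says this person "will contact the appropriate research physician if additional assessment is indicated": that sentence concerns clinical triage and does not say that other complaints go unrecorded.
- That lack of blinding is a further fault: in a single-arm study every assessor knows the treatment.

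What the reply does not remove is the absence of any stated path for an event judged unrelated, or the restricted question at the treatment visits. Symptom scores are not a record of events.

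**Conclusion.** The point holds as an inconsistency that should be resolved, together with a restriction in how events are collected. Section 9A does not expressly exempt serious unrelated events from reporting; it leaves two readings that give different answers for them, and the two parts must be reconciled. The adverse-event outcome is exposed mainly through the nurse's question. If events are missed there, the count of all events will be too low. It would be wrong to infer that the plan will report a particular understated rate, since the documents give nothing from which to predict how many events would be missed or misattributed.

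The conclusion assumes that the attached forms and the institutional policy do not already supply the missing definitions, which cannot be checked from these documents. The primary outcome is unaffected. The change is worth making because it is cheap and concerns safety reporting.

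**What to change.** 1. Reword step 2 so that every untoward event, whether volunteered or elicited, is recorded whatever its cause. The study physician then records seriousness, expectedness and relatedness as three separate fields.
2. State that the 48-hour report of a serious event neither waits for nor depends on the relatedness judgement. This brings the steps into line with the reporting rule.
3. Widen the nurse's inquiry, and the matching entries in the visit table, from reactions to treatment to any untoward event since the last visit.
4. In Section 3B, report the number and proportion of women with any event, and separately with any related event, among all women who had at least one session.

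The cost is a few reworded sentences, up to three added fields if the existing form lacks them, and brief physician review of each entry. The reported event count will probably be somewhat higher, because it will include events of the background disease; the separate relatedness field keeps those distinguishable.
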